## **4. Analysis populations**

### **4.1. Study population data sets**

Two study populations will be considered in the analysis as follows:

#### **Intent-to-Treat population**

Intent-to-treat (ITT) will be defined at the moment the randomisation is performed. For the ITT analysis in this trial, participants will be followed

with their ITT arms. For example, if a participant do not adhere to interventions, or receives the wrong treatment, they will be analyzed according to their primary allocations.

### **Per-protocol population**

Per protocol population will be defined after excluding participants who met the following situations:

Participants will be excluded from the per-protocol population if they:

- The primary outcome is missing (reversal of cardiometabolic abnormalities);
- Did not adhere to the allocated intervention, or switched intervention.

The treatment groups in the per-protocol analysis will be defined according to what the participant actually received. This population will be used for the supportive analyses.

### **4.2. Analysis Close Date**

The analysis close date is the date on which the last participant completed 2-week follow-up.

### **4.3. Data cleaning**

The data will be checked to ensure that there are no erroneous entries and that all missing data is properly coded. Any changes will be made on the ACCESS database.

### **4.4. Data download**

Once all data have been inputted and checked, the database will be locked and a data download request made. The data will be downloaded into STATA formats for statistical analyses.

## **5. Statistical Analyses**

### **5.1. Primary Outcome Analysis**

#### **5.1.1. ITT analysis of the primary outcome - the primary analysis**

The primary outcome is a binary composite outcome: occurrence of reversal outcome from any cardiometabolic abnormality at the 14th day after dietary intervention phase. The primary analysis will be based on the ITT population as defined above.

The primary endpoint will be summarised by number (%) of subjects that have reverse cardiometabolic abnormality by groups. Statistical analysis will be performed as a two-sided test, using chi-square test for detecting group difference of the percentage. If any subjects dropped off from the

primary endpoint, modified ITT analysis will be performed by using the available subjects.

A generalised linear model (GLM) will be used. In the GLM model, the occurrence of reversal outcome from any cardiometabolic abnormality at the 14th day after intervention phase will be treated as the response variable following a binomial distribution, the treatment as fixed effect and logit link function will be used. From this model, the reversal rate difference and its 95% CIs between two groups will be estimated.

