#### **Reversal of cardiometabolic abnormality is defined as:**

At the 14th day of dietary intervention phase, at least one of the following indicators changed from abnormal at baseline to normal: overweight, obesity, prediabetes, hyperlipidemia and elevated blood pressure.

(The reversal of overweight or obesity is defined according to references .

For subject with general obesity at baseline: weight loss of 1.5 kg after intervention;

For subject with central obesity at baseline: waist circumference reduction of 1.5 cm after intervention.)

Time Frame:

From the baseline (the first day of the intervention phase) to the 14th day of the intervention phase.

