### **3.4. Randomisation**

Randomisation is stratified by two age groups and with block size of 2 and allocation of 1:1 at each stratum. The randomisation was done by Stata software version 15. For each stratum a sequence of subjects IDs and intervention allocations was generated, which by creating a random variable and ordering on that variable. After signing the informed consent form, the subjects are assigned to the experimental or the control groups and receive the designed intervention.

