### **Covariate adjusted analysis of the primary outcome**

An analysis of the primary endpoint will be adjusted for age, sex, family history of cardiovascular disease, and fasting insulin concentrations at baseline by GLM model. The model may not converge when all covariates are introduced into the model simultaneously. If this occurs, a covariate will be removed from model one by one starting from the last covariate until the model converges.

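### Randomisation is stratified by age group, but the primary chi-square test and treatment-only GLM omit the stratum and give up some power, relative to a stratified analysis, if age group is prognostic

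*SAP*

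**What the plan says.** SAP Section 3.4: "Randomisation is stratified by two age groups and with block size of 2 and allocation of 1:1 at each stratum". The section does not give the age that separates the two groups.

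SAP Section 5.1.1 sets the primary test: "Statistical analysis will be performed as a two-sided test, using chi-square test for detecting group difference of the percentage". It adds a binomial GLM, in which "the treatment as fixed effect and logit link function will be used", and takes the effect estimate from it: "From this model, the reversal rate difference and its 95% CIs between two groups will be estimated". Neither method contains the age stratum. If subjects lack the primary endpoint, the available subjects are analysed.

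Age appears in two other places. Under the heading for the covariate-adjusted analysis, the primary endpoint "will be adjusted for age, sex, family history of cardiovascular disease, and fasting insulin concentrations at baseline by GLM model". The SAP does not say whether age is continuous or the two randomisation groups. Section 5.1.2 plans a subgroup analysis split at age 18, without saying that this is the randomisation cut-point.

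**The concern.** Blocks of 2 within each age group force the arms to be almost exactly balanced on age group. If age group predicts reversal, that balance reduces the true variance of the rate difference. An analysis that ignores the stratum still uses the larger, unbalanced-design variance. Its p-value and interval are then conservative, and the precision that the stratification bought is not collected.

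At stake is some power and some interval width in what is likely to be a small trial. The covariate-adjusted GLM and the subgroup analysis do not recover it for the primary result. The first is a separate model with three further covariates and an unspecified form of age. The second compares arms within age groups and gives no overall stratified test.

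**Working it through.** **Inputs from the SAP.** Two age strata, 1:1 in blocks of 2 (Section 3.4); unstratified two-sided chi-square test and treatment-only logit GLM (Section 5.1.1). The 5% level is implied by the two-sided test and 95% CI.

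**Assumed, because the documents give no figure.** 20 to 60 per arm; equal strata; exact balance; no dropout; 20-point effect. Control rates are centre ± gap/2. Set A is centred on 50%, with treated rates capped at 99% (this binds only at the 60-point gap, where the average effect is 19.5 points). Set B is centred on 40%. There is no sample-size or power figure in the plan to reproduce.

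**Step 1: size by approximation.** With stratum share w, overall rate p and age gap d, the true variance divided by the variance the chi-square test uses is

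1 − w(1−w)d² / [p(1−p)].

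For w = 0.5, p = 0.5, d = 0.3 this is 1 − 0.25 × 0.09 / 0.25 = 0.91. The unstratified interval is 1/√0.91 = 1.048 times as wide as needed, about 5%. The true type I error is 2Φ(−1.96/√0.91) = 4.0%.

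**Step 2: exact power.** All outcomes of the four stratum-by-arm binomials were enumerated, without continuity correction. With n per arm, m per arm per stratum, D = treated minus control reversals, S = total reversals and p̄ = S/(2n):

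- Chi-square = (D/n)² / [2p̄(1−p̄)/n]
- CMH = (ΣD_h/2)² / ΣV_h, with V_h = S_h(2m−S_h) / [4(2m−1)]

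Power (%), chi-square / CMH:

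| Set, n per arm | gap 0 | 20 | 30 | 40 | 60 |
|---|---|---|---|---|---|
| A, 20 | 24.5 / 23.3 | 23.9 / 24.9 | 23.1 / 26.7 | 22.0 / 28.9 | 16.9 / 34.1 |
| A, 30 | 35.1 / 35.2 | 34.7 / 36.1 | 34.2 / 38.1 | 33.3 / 41.4 | 28.7 / 49.9 |
| A, 40 | 45.8 / 45.8 | 45.7 / 46.3 | 45.5 / 47.9 | 45.1 / 51.9 | 41.7 / 62.8 |
| A, 60 | 61.8 / 61.6 | 62.0 / 62.7 | 62.3 / 65.5 | 62.7 / 69.9 | 61.4 / 80.6 |
| B, 20 | 22.2 / 22.0 | 21.6 / 23.3 | 20.8 / 25.0 | 19.6 / 27.5 | 15.7 / 35.6 |
| B, 30 | 35.0 / 35.0 | 34.6 / 35.2 | 34.1 / 36.6 | 33.4 / 39.6 | 30.7 / 50.3 |
| B, 40 | 45.8 / 45.8 | 45.7 / 45.8 | 45.5 / 46.7 | 45.2 / 49.9 | 44.2 / 63.2 |
| B, 60 | 61.2 / 61.2 | 61.4 / 61.6 | 61.7 / 63.2 | 62.2 / 67.4 | 63.8 / 80.0 |

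The power given up is therefore at most 1.7 points for gaps up to 20, 1.3 to 4.3 at 30, 4.7 to 8.1 at 40, and 16 to 21 at 60. With 80/20 strata at 30 per arm it is 0.7 to 3.6, 2.6 to 6.4 and 11 to 23 at gaps of 30, 40 and 60.

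**Step 3: type I error.** At 30 per arm, Set A, gaps 0/20/30/40/60: chi-square 5.19/4.72/4.15/3.38/1.51%; CMH 5.21/4.93/4.86/4.97/5.01%. Over 20 to 60 per arm with gaps up to 20, the chi-square test ranges from 3.8% to 5.7%. CMH also reaches 5.7%, so the small excess comes from discreteness and not from omitting the stratum.

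**Step 4: intervals.** 30 per arm, Set B, gaps 0/20/30/40/60. The planned interval is read as a delta-method interval from the treatment-only GLM.

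| Interval | Coverage (%) | Mean width |
|---|---|---|
| Planned, unstratified | 93.4/93.9/94.6/95.6/97.9 | 0.487 to 0.490 |
| Unstratified Newcombe | not needed here | 0.461 to 0.464 |
| Stratified Newcombe | 94.9/94.8/94.9/95.4/96.3 | 0.455/0.447/0.437/0.424/0.397 |

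Like for like (Newcombe against Newcombe), the stratum itself narrows the interval by about 1/3/5/8/14%.

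**The case against.** The best defence is that nothing in the documents shows harm. They give no reversal rates by age, and every figure above rests on assumed inputs. For gaps up to 20 points the two tests are nearly the same. The covariate-adjusted GLM already includes age and lists it first, so under the rule for non-convergence it would be the last covariate dropped. All of that stands, and it limits the priority. It does not change the primary p-value or interval, which still ignore the stratum.

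Four stronger readings are tempting and not supported:

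- *The primary test is invalid.* It is not. At large gaps it errs on the conservative side, so a positive result would stand.
- *There is a threshold at a 30-point gap.* The loss grows smoothly, and 30 points is only where it becomes noticeable under these assumptions.
- *The chi-square test's own power falls as the gap widens.* The loss is relative to CMH. In Set B at 60 per arm, chi-square power rises slightly, from 61.2% to 62.2% at a gap of 40.
- *One fixed reversal threshold for everyone aged 9 to 30 implies an age gap.* The 1.5 kg rule is limited: "For subject with general obesity at baseline: weight loss of 1.5 kg after intervention". The 1.5 cm rule likewise covers only central obesity. Subjects who enter through prediabetes, lipids or blood pressure alone have neither threshold.

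It is also fair to say that most of the difference in width between the planned interval and a stratified Newcombe interval at small gaps comes from the interval method and not from the stratum.

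**Conclusion.** The mismatch between the randomisation and the primary analysis is real. Its consequence is lost efficiency if age group is prognostic, not a false-positive risk. The size depends on an age gap that the documents neither state nor rule out: negligible up to about 20 points, modest at 30 to 40, and large only at an extreme gap such as 60. These figures assume equal strata, a 20-point effect, 20 to 60 per arm and complete data. This is a cheap improvement of modest priority for a pilot.

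**What to change.** - In Section 5.1.1, make the primary test a two-sided CMH test stratified by the age group used at randomisation.
- Report the stratum-size-weighted rate difference with a stratified 95% CI as the lead interval, and name the version. One suitable choice is stratified Wilson limits for each arm with stratum-size weights, combined by Newcombe's square-and-add rule. A stratified delta-method interval is a poorer lead, because it covers only 92.5% to 93.7% at 20 to 30 per arm.
- State the age cut-point in Section 3.4 and add the randomisation stratum to the variable list in Section 8, which has age and birth date but no stratum.
- Keep the chi-square test and the covariate-adjusted GLM as sensitivity analyses.

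**Cost.** Wording, plus one variable that must already exist in the randomisation list. With complete data and equal arms within each stratum, the weighted difference equals the crude difference, so the estimate does not change. With dropout the two can differ, and the weighted one keeps the age balance.

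**Downside.** If age group is not prognostic, CMH loses power at 20 per arm. With a 50% control rate this is 1.3 points for a 20-point effect (24.5% to 23.3%, before rounding) and 2.4 points for a 30-point effect (53.1% to 50.7%). In the settings checked at 30 per arm or more, the loss is about 0.2 points or less.

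### The primary endpoint is tested by chi-square, but its confidence interval comes from a logit model, so in a small trial the interval can exclude zero when the test is not significant

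*SAP*

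**What the plan says.** SAP section 5.1.1 carries the label of primary analysis and fixes the population: "The primary analysis will be based on the ITT population as defined above". If outcomes are missing, a "modified ITT analysis will be performed by using the available subjects".

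It then gives two outputs for the same endpoint:

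- A test: "Statistical analysis will be performed as a two-sided test, using chi-square test for detecting group difference of the percentage". Continuity correction and significance level are not mentioned.
- A binomial GLM, in which "the treatment as fixed effect and logit link function will be used". Its product is an estimate: "From this model, the reversal rate difference and its 95% CIs between two groups will be estimated".

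Under its own subheading, before 5.1.2, the SAP adds a third: "An analysis of the primary endpoint will be adjusted for age, sex, family history of cardiovascular disease, and fasting insulin concentrations at baseline". Covariates are dropped from the end of the list if this model does not converge. The SAP does not state the role of this analysis or the effect measure it will report. The SAP does use a label of this kind in section 4.1, for the per-protocol population: "This population will be used for the supportive analyses".

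**The concern.** A reader of the results will see a chi-square p-value and a 95% interval for the rate difference side by side, and will expect them to agree on whether zero is compatible with the data. A logit model does not give a rate difference directly. The usual route, a delta-method marginal difference, uses a different variance from the chi-square test. If the two disagree on a borderline result, the SAP does not say which one stands.

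Two things are at stake. The interval may have less than its stated 95% coverage at pilot sizes. And with equal arms every disagreement points towards a positive reading. The adjusted model can also differ from the chi-square result, and the SAP does not say what weight it would then carry.

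**Working it through.** **Inputs from the SAP.** Two-sided chi-square test, logit GLM with treatment only, rate difference with 95% CI (5.1.1); 1:1 allocation (3.4). The plan states no sample size, expected rate, power or alpha, so it has no figure to reproduce.

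**Assumptions.** 10 to 50 per arm; common reversal rate 0.3 to 0.8 under the null; two-sided 5%, inferred from the 95% CI; no continuity correction; delta method for the rate difference.

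**Step 1: the two variances.** Let n be the number per arm, p1 and p2 the observed rates, d = p1 − p2 and p̄ = (p1 + p2)/2.

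- Chi-square: z = d/√V_pool, with V_pool = 2p̄(1 − p̄)/n.
- Treatment-only logit model: the fitted logit in an arm has standard error 1/√(np(1 − p)). Multiplying by p(1 − p) gives √(p(1 − p)/n). The difference therefore has V_unp = [p1(1 − p1) + p2(1 − p2)]/n.
- Subtracting: V_pool − V_unp = d²/(2n), which is never negative.

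So with equal arms the interval excludes zero whenever the chi-square test is significant, and sometimes when it is not.

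**Step 2: worked example, 13/20 v 7/20.** d = 0.65 − 0.35 = 0.30 and p̄ = 0.50.

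- V_pool = 2(0.25)/20 = 0.0250; SE 0.1581; z = 1.897; p = 0.058.
- V_unp = (0.2275 + 0.2275)/20 = 0.02275; SE 0.1508; interval 0.30 ± 1.96 × 0.1508 = 0.004 to 0.596.
- Check: 0.0250 − 0.02275 = 0.00225 = 0.30²/40.

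Other tables that split in the same way:

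| Table | Chi-square p | Interval for the difference |
|---|---|---|
| 8/10 v 4/10 | 0.068 | 0.8% to 79.2% |
| 24/30 v 17/30 | 0.052 | 0.5% to 46.1% |
| 20/50 v 11/50 | 0.052 | 0.2% to 35.8% |

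**Step 3: how often under the null.** Exact enumeration of two binomials; the ranges are over common rates of 0.3 to 0.8.

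| Per arm | Interval excludes zero | Chi-square rejects |
|---|---|---|
| 10 | 8.8-9.5% | 3.0-4.2% |
| 15 | 5.1-6.7% | 4.6-5.5% |
| 20 | 6.5-8.1% | 4.3-5.3% |
| 25 | 5.9-6.5% | 5.4-6.5% |
| 30 | 5.2-6.0% | 4.9-5.2% |
| 35 | 5.4-7.2% | 4.3-5.1% |

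At 40 and 50 per arm the two are close; at a 50% rate both reject in 5.7% of null trials. In no setting did the chi-square test reject while the interval included zero. The row for 10 per arm is the least secure. It applies the V_unp formula even when an arm has no reversals or only reversals, where the logit model has no finite estimate.

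**Step 4: how often when there is an effect.** At true rates of 60% v 40%, the exact probability that the test and interval disagree is 9.7% at 20 per arm, 0.06% at 30, below 0.01% at 50 and 1.5% at 75. If the chi-square test is continuity-corrected, it is 18.7% at 20, 9.3% at 30 and 8.1% at 50. The correction should therefore be settled in the text.

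**Step 5: the adjusted model.** This was simulated with 3,000 trials per setting at 20, 30 and 50 per arm, four covariates with assumed effects of 0 or 0.5 per unit on the logit scale, and the treatment coefficient as the adjusted result. Chi-square and the adjusted model disagreed in about 2-4% of null trials, and in about 6-12% when the log odds ratio was 0.9. These figures show only that the two can differ, because they depend on the assumed covariate effects.

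**Step 6: which interval matches the test.** A score interval inverts a test that estimates the rates under each candidate difference. At zero difference these estimates equal p̄, so the Mee statistic is the Pearson z of Step 1. Miettinen-Nurminen multiplies the variance by N/(N − 1), where N is the total number in both arms, and can contradict Pearson. For 13/15 v 8/15, z = 0.3333/0.1673 = 1.992 (p = 0.046), but 1.992 × √(29/30) = 1.959 (p = 0.0502), so that interval includes zero.

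**The case against.** The strongest reply is that 5.1.1 already implies the roles. Chi-square is the only procedure called a test, and the GLM is there to estimate. That is an ordinary pairing and the fair reading. A reader might go further and infer that the SAP sets up three competing primary analyses, with an inflated false-positive rate for quoting whichever is favourable. The documents do not support that:

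- The adjusted model stands under its own subheading, so its place within the primary analysis rests on layout alone.
- No adjusted rate difference is promised. The one in 5.1.1 is tied to the treatment-only model.
- Choosing among the results after the fact is not a planned procedure. Any error rate for it would rest on assumed covariate effects and an assumed adjusted output, so no single figure should be claimed.

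It is also fair to say that the test and the unadjusted interval seldom conflict at several plausible sizes, that the chi-square test itself exceeds 5% in places (up to 6.5% at 25 per arm), and that one significance verdict carries limited weight in a pilot.

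What remains is narrower. The implied roles are not stated, the adjusted model has none, and stating them would still leave an interval that can contradict the test and undercovers at some small sizes.

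**Conclusion.** The point holds as a minor one. The interval in 5.1.1 does not match the test in 5.1.1. With equal numbers analysed, every mismatch has the interval excluding zero and the test not significant. The size depends on n: clear at 10 and 20 per arm, moderate at 35, small at 15, 25 and 30, and close to nil at 40 and 50.

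This rests on the delta method, an uncorrected chi-square test, a two-sided 5% level, and assumed sample sizes and rates; the documents give none of these. The one-way direction also needs equal arms. The available-subjects rule for missing outcomes could make the arms unequal, and the algebra in Step 1 then no longer guarantees it.

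**What to change.** Make two changes in SAP section 5.1.1:

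1. Replace the model-based interval with the Mee score interval for the unadjusted rate difference. Do not substitute Miettinen-Nurminen, for the reason in Step 6.
2. State that the two-sided 5% Pearson chi-square test without continuity correction, in the ITT population, decides the primary comparison, and that the covariate-adjusted GLM is supportive.

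If the sponsor prefers a different deciding test, the interval should be taken from that same test.

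The cost is a few lines of SAP text and a short routine for the interval. The interval will be slightly wider in some small samples, and a favourable adjusted result could not serve as the primary claim. The change gives one consistent answer from test and interval; it does not guarantee an error rate of exactly 5%.

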### **Covariate adjusted analysis of the primary outcome**

An analysis of the primary endpoint will be adjusted for age, sex, family history of cardiovascular disease, and fasting insulin concentrations at baseline by GLM model. The model may not converge when all covariates are introduced into the model simultaneously. If this occurs, a covariate will be removed from model one by one starting from the last covariate until the model converges.

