**Effects of intermittent caloric restriction in youth with
cardiometabolic risk: a randomized controlled pilot study**

Supplementary Research Ethics Board Approval

NCT number: NCT04011995

September 20, 2019

**Effects of intermittent caloric restriction in youth with cardiometabolic risk:
a randomized controlled pilot study**

Supplementary Research ethics board approval

This is a randomized controlled pilot study to evaluate the effects of intermittent caloric restriction compared with low carbohydrate diet in youth with cardiometabolic risk. Total trial duration for individual subject is one month consisting of a 14-day intervention phase and a 14-day self-maintenance phase.

In the previous study protocol, the eligible subjects were defined as pre-diabetic youth aged 13 to 30 years old which were high risk population for cardiometabolic diseases. The study was approved by the Research Ethics Committee of the Children's Hospital of Fudan University (CHFU 2017 No. 228) in December 2017.

In 2019, we adjusted the inclusion criteria and expanded the age range of the eligible subjects after discussion by the study team.

The adjusted inclusion criteria are as follows:

- (1) Aged 9-30 years old;
- (2) With at least one of the following cardiometabolic risk:
 - Overweight or obesity (central obesity or general obesity);
 - Prediabetes: impaired fasting glucose and/or impaired glucose tolerance;
 - Dyslipidemia;
 - Elevated blood pressure.

The previous subjects and the adjusted subjects were from the same population, and previous subjects were part of the adjusted study subjects. The protocol after adjusting the subjects was also approved by the Research Ethics Committee of the Children's Hospital of Fudan University (CHFU 2019 No. 216) in June 2019.

RESEARCH ETHICS BOARD APPROVAL

PROTOCOL TITLE: Effects of Intermittent Caloric Restriction on Glucose Regulation and Related Gene Methylation in Youth Pre-diabetic Youth

PRIMARY INVESTIGATORS: [name] PROTOCOL TYPE: Lifestyle intervention study

APPLICATION INSTITUTIONS: Children's Hospital of Fudan University

STARTING AND ENDING DATES: 2018.1—2020.12

NAME LIST OF RESEARCH ETHICS BOARD: [name]; [name]; [name]; [name]; [name]; [name]; [name]; [name]; [name]; [name]

THE FOLLOWING ITEMS ARE COMPLETED BY RESEARCH ETHICS BOARD:

DOCUMENTS: (CLICK ✓ BEFORE OPINION)

(✓) protocol
(✓) application form
(✓) informed and consent form
() relevant approvals

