## 2.2. Outcomes

### 2.2.1. Primary outcome

#### **Reversal (%) of cardiometabolic abnormality.**

The primary outcome is a composite outcome that will be measured as any reverse ~~outcome~~ of the following cardiometabolic abnormality: (1) overweight or obesity, (2) prediabetes, (3) hyperlipidemia or (4) elevated blood pressure. It is defined as occurring if any cardiometabolic abnormality of individual subject has a reversal outcome after 14 days dietary intervention (measured at the 14th day).

The primary endpoint will be summarised by number (%) of subjects that with at least one reverse of cardiometabolic abnormalities.

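### The supplementary adjusted analysis of the primary outcome omits the number of baseline abnormalities, which the any-reversal definition makes a determinant of success

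*SAP*

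**What the plan says.** **Who enters.** The adjusted inclusion criteria in the Protocol admit a subject "With at least one of the following cardiometabolic risk" out of four classes: overweight or obesity, prediabetes, dyslipidaemia and elevated blood pressure. Subjects may therefore differ in how many they have.

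**What counts as success.** SAP 2.2.1 makes the endpoint binary: "It is defined as occurring if any cardiometabolic abnormality of individual subject has a reversal outcome after 14 days dietary intervention". The definition that follows requires that "at least one of the following indicators changed from abnormal at baseline to normal", so only abnormalities present at baseline can contribute. Excess weight has its own rules, by two separate routes: "For subject with general obesity at baseline: weight loss of 1.5 kg after intervention" and "For subject with central obesity at baseline: waist circumference reduction of 1.5 cm after intervention".

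**How it is analysed.** In SAP 5.1.1 the primary analysis is an unadjusted two-sided chi-square test, with a binomial GLM that has treatment as its only term and is meant to yield a rate difference with a 95% CI. A further analysis is "adjusted for age, sex, family history of cardiovascular disease, and fasting insulin concentrations at baseline by GLM model". If that model fails to converge, covariates are removed one at a time from the end of the list.

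**What else could deal with it.** Randomisation (SAP 3.4) is stratified by two age groups only. The one subgroup analysis (SAP 5.1.2) is by age. The baseline measurements that define each abnormality, together with sex and age, are in the variable list (SAP 8).

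**The concern.** The number of baseline abnormalities equals the number of ways a subject can meet the endpoint. This link comes from the endpoint's own definition and needs no outside evidence of prognosis. Family history and fasting insulin, which are in the model, have no such built-in link.

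Two things are at stake. First, outcome variance that a baseline covariate could explain stays in the error term. Second, in a small trial the arms can differ by chance in the average number of abnormalities. The adjusted analysis is the only place in the SAP where such an imbalance could be handled, and as listed it would not be. Adding the term after an imbalance has been seen would be post hoc, so it needs to be specified in advance.

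**Working it through.** The plan states no sample size, power, reversal rate or distribution of baseline abnormalities, so there is no figure of its own to reproduce. Everything below uses assumed inputs, shown as ranges.

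**Assumptions.** Each baseline abnormality reverses with probability *p* (0.1 to 0.4), independently of the others. The baseline count *k* runs from 1 to 4 (the four classes), with three assumed distributions for k = 1/2/3/4: A 50/30/15/5%, B 25/25/25/25%, C 70/20/8/2%. Arms are equal, with 20 to 50 per arm.

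**Step 1: dependence on the count.** P(any | k) = 1 − (1 − p)^k.

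| p | k=1 | k=2 | k=3 | k=4 |
|---|---|---|---|---|
| 0.1 | 0.10 | 0.19 | 0.27 | 0.34 |
| 0.2 | 0.20 | 0.36 | 0.49 | 0.59 |
| 0.3 | 0.30 | 0.51 | 0.66 | 0.76 |
| 0.4 | 0.40 | 0.64 | 0.78 | 0.87 |

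**Step 2: variance explained.** R² = Var[P(any | k)] / [m(1 − m)], where m is the mean success rate.

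- Example, A at p = 0.3: m = 0.5(0.300) + 0.3(0.510) + 0.15(0.657) + 0.05(0.760) = 0.440. The variance of P(any | k) is 0.0234, and R² = 0.0234/0.246 = 0.095.
- B at p = 0.3 gives 0.121, and C gives 0.072.
- Over p = 0.1 to 0.4 and all three distributions, R² runs from 0.032 (C, p = 0.1) to 0.144 (B, p = 0.4), so about 3–14%.

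**Step 3: chance imbalance against total sampling error.** With no treatment effect and n per arm, the SD of the shift due to imbalance in the count is √(2·Var[P(any | k)]/n). The SD of the whole unadjusted rate difference is √(2m(1 − m)/n).

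| p = 0.3, n = 20 per arm | Shift from count | Total SD | SD with count removed | Reduction |
|---|---|---|---|---|
| A | 4.8 points | 15.7 | 14.9 | 4.9% |
| B | 5.5 points | 15.7 | 14.7 | 6.2% |

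The third SD column is √(total² − shift²), for example √(15.7² − 4.8²) = 14.9. At 40 per arm the shift has an SD of 3.4 (A) to 3.9 (B) points against a total of 11.1.

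By simulation at p = 0.3 over the three distributions, the shift is at least 5 points in 22–36% of trials at 20 per arm and in 5–15% at 50 per arm.

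**Step 4: gain from adjustment.** The large-sample reduction in SD is 1 − √(1 − R²). That is 1.6% at R² = 0.032 and 7.5% at R² = 0.144. Simulated logistic models with a standardised rate difference (p from 0.2 to 0.35, distributions like A and B, 20 to 50 per arm), comparing no adjustment with adjustment for the count alone, gave reductions of about 2–6%. At 30 per arm, for example, the SD fell from 0.1212 to 0.1191 (1.7%, A, p = 0.2) and from 0.1294 to 0.1223 (5.5%, B, p = 0.3). With an assumed 50% against 75% reversal at 20 per arm, power moves from 37% to 38–42% for R² of 0.03 to 0.15.

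**Step 5: correlated reversals.** One diet acts on all components, so independence is generous. In a shared-factor probit model at p = 0.3, for distributions A and B, R² falls to 6–7% at a latent correlation of 0.3 and to 4–5% at 0.5. The SD reduction is then about 2–4%.

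**Limit of the illustration.** These figures use a count of 1 to 4. The SAP gives general and central obesity separate rules, so the number of routes can reach 5; at p = 0.3 that adds P(any | 5) = 1 − 0.7⁵ = 0.83.

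**The case against.** The strongest reply has five parts.

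- **It is not the primary analysis.** A reader might infer that the primary result rests on a misspecified model. The text does not support that. The primary test and its GLM contain treatment only, the covariate list belongs to a supplementary analysis, and changing the list leaves the primary result as it is. This stands. It also means that the adjusted model is the only one that could deal with the imbalance.
- **Randomisation already protects the comparison.** A reader might infer bias or an inflated type I error. Neither follows. Under 1:1 randomisation the omission causes no bias on average and no unconditional inflation of the error rate. Nor is the shift of up to about 11 points at 2 SD (2 × 5.5, at 20 per arm) additional error: it is already part of a total of about 31 points at 2 SD (2 × 15.7). This stands in full.
- **The gain is small and rests on assumptions.** This also stands. If the chance of reversing each abnormality falls as abnormalities accumulate, the gain shrinks further.
- **Extra terms cost something.** The SAP already expects that four covariates may not converge. This argues for one added term and no more.
- **Choice of covariates is a judgement, and baseline insulin may stand in for the count.** Partly so. But insulin is last in the list and is the first to be dropped, whereas the count is tied to the outcome by definition.

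**Conclusion.** The point holds as a cheap improvement to a supplementary analysis. The any-reversal definition makes the number of baseline abnormalities a determinant of the outcome, and no part of the design or analysis uses it. The documents do not support a claim that the primary comparison is biased or invalid.

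The loss is modest: about 3–14% of outcome variance, and roughly a 2–6% larger SD of the rate difference than is necessary. These figures assume independent reversals, per-abnormality probabilities within 10–40% and the illustrative distributions above; positive correlation reduces them. In a small pilot, uncorrected imbalance in the realised sample is the better reason to act. Without a stated sample size, reversal rate or distribution of abnormalities, no single figure can be given.

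**What to change.** In the covariate-adjusted analysis in SAP 5.1.1, add one covariate directly after age: the number of baseline abnormalities eligible for reversal, entered as a linear term. Count general overweight/obesity, central obesity, prediabetes, dyslipidaemia and elevated blood pressure as one each (range 1 to 5). The two obesity types are counted separately because SAP 2.2.1 gives each its own reversal rule; a count of the four classes would score a subject with both as having only one route. Derive the count from the baseline variables in SAP 8, including sex and age, which the cut-offs require.

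State that the adjusted rate difference and its CI come from standardisation (margins) after the logit model. The gain in precision applies to that marginal difference, which is the SAP's effect measure; the standard error of a conditional log odds ratio would not fall.

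Do not add a separate overweight/obesity indicator. It overlaps the count and may be nearly constant in this population.

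**Cost.** A sentence or two in the SAP and one derived variable, with no new data. The downside is one more term in a model that may already fail to converge. Under the existing removal rule, insulin, family history and sex would all be dropped before the count, and the sponsor should accept that order knowingly.
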